#### **Statistical methods:**

This study will be conducted in 2 parts. A total of approximately 192 subjects (64 subjects per treatment arm) are planned for randomization in Part 1, and approximately 192 subjects (64 subjects per treatment arm) are planned for randomization in Part 2, for a total of 384 subjects to be randomized. This sample size is based on a dose-ranging scheme to evaluate initial safety, efficacy, of RTA 901 in this subject population. The primary comparisons for efficacy are between each of the RTA 901 treatment groups and the placebo treatment group. The overall Type I error rate will be controlled at the 0.05 significance level using a hierarchical testing strategy that will be defined in the Statistical Analysis Plan. Power calculations are based on a 2-sample t-test with no adjustments for multiple comparisons. The study assumes a mean difference in NPRS pain intensity of 1.2 between each RTA 901 treatment group and placebo and a standard deviation of 2.4.

If doses selected for Part 2 do not include doses studied in Part 1, then an analysis by dose group for Part 1 or Part 2 doses will be performed following completion of each study part. With 64 subjects per treatment group, each study part has 80% power to compare treatment groups to placebo.

If doses selected for Part 2 include any doses studied in Part 1 (ie, 10 or 80 mg), then an analysis by dose group will be performed using Part 1 and Part 2 combined, following completion of the study. The dose group that is enrolled in both parts will have 128 subjects. With 128 placebo subjects compared to 128 subjects in the RTA 901 dose group, there is 98% power to detect the same difference (1.2 NPRS points) assuming the same standard deviation (2.4). RTA 901 dose groups that are enrolled in only 1 part will have 64 subjects. With 128 placebo subjects compared to 64 subjects in each RTA 901 dose group, there is 90% power to detect the same difference (1.2 NPRS points) assuming the same standard deviation (2.4).

The intent-to-treat analysis set is defined as all randomized subjects categorized by their randomized treatment group (whether or not they received study drug). The analysis population for the efficacy endpoints is the intent-to-treat population. Mixed-model repeated measures analyses will be used to analyze the primary efficacy endpoints. A detailed Statistical Analysis Plan will be developed prior to database lock.

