## 3.6. Part 2 Dose Selection Process

A Dose Selection Committee (DSC) comprised of Sponsor personnel and an external pharmacometrics consultant will select the 2 doses of RTA 901 for Part 2 using data from Part 1. An E-R analysis for efficacy will be conducted with efficacy data from all subjects up to Week 12 of treatment in Part 1 and provide a dosing recommendation for Part 2 to the DSC. The selected doses will be documented in a Note-to-File to the Investigators and IRBs (as appropriate) and will not require a protocol amendment.

It is possible that enrollment in Part 2 of the study may begin while some Part 1 subjects are completing their remaining study visits. Subjects enrolled in Part 1 will not be eligible for enrollment in Part 2.

Details of the membership, objectives, and process to be followed by the DSC will be described in a separate charter. Additionally, a separate data management and analysis plan supporting this activity will be created. Results will be reported in a separate standalone report, outside the clinical study report (CSR).

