# 4.5. Subject Enrollment and Randomization

Following a Screening Period of up to 2 weeks, eligible subjects will be enrolled and enter a single-blind placebo Run-in Period (14± 2 days). Subjects in Part 1 who remain eligible (according to Randomization eligibility criteria) will be randomized 1:1:1 to either RTA 901 (10 or 80 mg) or placebo at Day 1, and subjects in Part 2 who remain eligible will be randomized 1:1:1 to either RTA 901 (Dose 1 or Dose 2) or placebo at Day 1 (see Table 3). Approximately 192 eligible subjects (64 subjects per treatment arm) will be enrolled in Part 1, and approximately 192 eligible subjects (64 subjects per treatment arm) will be enrolled in Part 2. Randomization within each part will be stratified using RTSM into 2 strata based on approved

SOC pain medication. One stratum will include subjects taking duloxetine, while the other stratum will include subjects taking pregabalin or gabapentin.

**Table 3:** Treatment Arms by Study Part

Study Part	Treatment Arms					
Part 1 (N=192)	10 mg RTA 901 (N=64)	80 mg RTA 901 (N=64)	Placebo (N=64)			
Part 2 (N=192)	Dose 1 RTA 901 (N=64) (selected from dose range of 1 to 80 mg) a	Dose 2 RTA 901 (N=64) (selected from dose range of 1 to 80 mg) a	Placebo (N=64)			

Abbreviations: E-R=exposure-response

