#### 7.8.3. Rescue Medication

Rescue medication for DPNP is in addition to standard of care medication (gabapentin, pregabalin or duloxetine) for DPNP. Rescue medication is intended to treat temporary elevations in a subject's DPNP and is intended to be used occasionally and not meant to be used for prolonged periods of time.

Subjects who enter screening after implementation of protocol Version 4.0 may only use acetaminophen as a rescue medication for DPNP as needed. If rescue medication is needed for DPNP, subjects will be instructed to take acetaminophen 500 mg every 4 to 6 hours as needed (not to exceed 3000 mg per day).

Subjects currently in the study at the time of implementation of protocol Version 4.0 using ibuprofen as rescue medication for DPNP may switch their rescue medication to acetaminophen (i.e., no longer use ibuprofen as a rescue medication for DPNP) or continue to use as rescue medication for DPNP ibuprofen 200 to 400 mg every 4 to 6 hours as needed (not to exceed 600 mg/day) for up to 3 days in a 7-day period (not calendar week). Subjects unable to comply with these conditions will need to discontinue study treatment and withdraw from the study; some or all of such subjects may be replaced at the discretion of the Sponsor.

The daily maximum dosages stated in this section are inclusive of those used outside of treatment for DPNP. Any questions related to rescue medications should be directed to the Medical Monitor prior to administration when possible.

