### 8. STATISTICS

### 8.1. Sample Size Estimate

This study will be conducted in 2 parts. A total of approximately 192 subjects (64 subjects per treatment arm) are planned for randomization in Part 1 and approximately 192 subjects (64 subjects per treatment arm) are planned for randomization in Part 2, for a total of 384 subjects to be randomized. This sample size is based on a dose-ranging scheme to evaluate initial safety, efficacy, of RTA 901 in this population. The primary comparisons for efficacy are between each of the 2 RTA 901 treatment groups and the placebo treatment group. The overall Type I error rate will be controlled at the 0.05 significance level. A hierarchical testing strategy to control the overall Type I error will be defined in the SAP. Power calculations are based on a 2-sample t-test with no adjustments for multiple comparisons. The study assumes a difference in NPRS pain intensity means of 1.2 between each RTA 901 treatment group and the placebo treatment group and a standard deviation of 2.4.

If doses selected for Part 2 do not include doses studied in Part 1, then an analysis by dose group for Part 1 or Part 2 doses will be performed following completion of each study part. Within each Part, with 64 subjects per treatment group, each study part has 80% power to compare treatment groups to placebo.

If doses selected for Part 2 include any doses studied in Part 1 (ie, 10 or 80 mg), then an analysis by dose group will be performed using Part 1 and Part 2 combined, following completion of the study. The dose group that is enrolled in both parts will have 128 subjects. With 128 placebo subjects compared to 128 subjects in the RTA 901 dose group, there is 98% power to detect the same difference (1.2 NPRS points) assuming the same standard deviation (2.4). RTA 901 dose groups that are enrolled in only 1 part will have 64 subjects. With 128 placebo subjects compared to 64 subjects in each RTA 901 dose group, there is 90% power to detect the same difference (1.2 NPRS points) assuming the same standard deviation (2.4).

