# 8.3. Endpoints and Objectives

The SAP will describe in detail the methods used for the primary, safety, secondary, and exploratory endpoints and will serve as the final arbiter of all statistical analyses. The study endpoints are listed in Section 2.2.

Data will be summarized using descriptive statistics. Continuous data will be summarized with statistics such as mean, standard deviation, median, minimum, and maximum. Categorical data will be summarized using frequency counts and percentages.

If doses selected for Part 2 include any doses studied in Part 1 (ie, 10 or 80 mg), then the final analysis by dose group will be performed following final study database lock. Otherwise, if doses selected for Part 2 do not include doses studied in Part 1 then final analysis by dose group for Part 1 or Part 2 doses will be performed following the Part 1 or Part 2 database lock, respectively.

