### 8.4.3. Analysis of the Primary Variable(s)

The primary analysis will be performed using mixed model repeated measures (MMRM), and detail of the MMRM model will be specified in the SAP. Within the framework of the MMRM model, estimate and 95% CIs will be calculated for the mean changes within each treatment group as well as for the differences in mean changes relative to the placebo.

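### If Part 2 repeats one Part 1 dose, a dose studied in a single part is compared with placebo pooled over both sequential parts; the stated 90% power assumes equal placebo response, and no adjustment for part is planned

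*Protocol*

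**What the plan says.** Protocol 8.1 distinguishes two cases. If Part 2 uses only new doses, each part is analysed on its own. If Part 2 includes 10 or 80 mg, "then an analysis by dose group will be performed using Part 1 and Part 2 combined, following completion of the study". Section 8.3 repeats the condition: "then the final analysis by dose group will be performed following final study database lock". The synopsis adds that "RTA 901 dose groups that are enrolled in only 1 part will have 64 subjects", and both places give the power for such a dose: "With 128 placebo subjects compared to 64 subjects in each RTA 901 dose group, there is 90% power to detect the same difference". The power calculations use a two-sample t-test with a difference of 1.2 and a standard deviation of 2.4.

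The parts are randomised separately. Section 4.5 says: "Randomization within each part will be stratified using RTSM into 2 strata based on approved" standard-of-care pain medication. They are also essentially sequential, because the Part 2 doses depend on Part 1 results. Section 3.6 says: "An E-R analysis for efficacy will be conducted with efficacy data from all subjects up to Week 12 of treatment in Part 1". The same section allows Part 2 enrolment to begin while some Part 1 subjects finish their remaining visits.

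On the model, protocol 8.4.3 says only that "detail of the MMRM model will be specified in the SAP". The supplied SAP analyses Part 1 alone (SAP 5.1), its MMRM has no term for part (SAP 6.3), and it leaves Part 2 to a separate SAP (SAP 1).

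**The concern.** Suppose exactly one Part 1 dose is repeated. There are then two one-part doses: the Part 1 dose that was dropped and the new Part 2 dose. Each has 64 subjects and would be compared with 128 placebo subjects, 64 of whom were never randomised against it. Those 64 are non-concurrent controls, and randomisation does not protect that half of the comparison.

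The documents do not show that placebo response differs between parts, but they give reasons why it might. The rescue rule changed with protocol Version 4.0: "Subjects who enter screening after implementation of protocol Version 4.0 may only use acetaminophen as a rescue medication for DPNP as needed". Subjects already in the study could continue ibuprofen within limits (protocol 7.8.3), so Part 1 may span both rules while later screeners fall under one. SAP 1 also says that the Part 2 design may change after the Part 1 results.

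The choice of dose is what is at stake. A one-part dose whose estimate carries a between-part shift would be judged beside a repeated dose whose estimate does not. The choice of dose for later development could then partly reflect when a dose was studied.

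**Working it through.** **Inputs.** Difference 1.2, SD 2.4, 64 per arm per part (protocol 8.1); two-sided alpha 0.05 (SAP 2.4, for the same assumptions).

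**The plan's own figures.** A noncentral t calculation gives 80.1% for 64 v 64, 97.9% for 128 v 128 and 90.1% for 64 v 128. The protocol states 80%, 98% and 90%. All three reproduce.

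**Precision under three analyses.** Take six cells of 64: placebo, repeated dose S and dose A in Part 1; placebo, S and new dose Y in Part 2. Write P1, P2, S1, S2 for the cell means. All three reference means for Y give a standard error of the form 2.4 × √(k/64).

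- *Pooled placebo, no part term.* The reference is (P1 + P2)/2, so k = 1 + 1/2 = 1.5.
- *Additive part term.* The part effect is estimated as [(P2 − P1) + (S2 − S1)]/2. The reference for Y is (P1 + P2)/2 plus half of this, which is ¾P2 + ¼P1 + ¼S2 − ¼S1. So k = 1 + (9 + 1 + 1 + 1)/16 = 1.75.
- *Concurrent placebo only.* The reference is P2, so k = 2.

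| Analysis of a one-part dose | SE | Power (t) |
|---|---|---|
| Pooled placebo, unadjusted | 0.367 | 90.1% |
| Additive part term | 0.397 | 85.5% |
| Concurrent placebo only | 0.424 | 80.1% |

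The normal approximation for the part-adjusted case is Φ(1.2/0.397 − 1.96) = 85.6%. For the repeated dose, SE = 2.4 × √(2/128) = 0.300 and power is 97.9%, with or without the part term.

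**Bias without the part term.** Let the mean change shift by s between parts in every arm. For Y, the concurrent placebo mean minus the pooled placebo mean is P2 − (P1 + P2)/2, which has expectation s/2. For A the same difference is −s/2. The two one-part doses are therefore biased in opposite directions, and the contrast between them is off by the full s.

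**Consequences.** The documents give no value for s, so these values are assumed. With b = s/2 and SE 0.367, two-sided Type I error is Φ(−1.96 + b/0.367) + Φ(−1.96 − b/0.367). Power when the shift goes against the drug is Φ((1.2 − b)/0.367 − 1.96).

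| Assumed s | Bias | Type I error, unadjusted | Adverse-shift power, unadjusted |
|---|---|---|---|
| 0.2 | 0.10 | 5.9% | 85% |
| 0.5 | 0.25 | 10.4% | 73% |
| 1.0 | 0.50 | 27% | 48% |

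A shift in the other direction raises apparent power instead, for example to 97.5% at s = 0.5.

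**Simulation check.** The same six arms were simulated with the shift added to all Part 2 arms, 40,000 trials per cell, at s = 0.2, 0.5 and 1.0. With the part term, Type I error was 4.7%, 4.9% and 4.9%, and power was 85.3%, 85.2% and 85.7%. Without it, Type I error was 5.5%, 10.4% and 26.3%, and power was 84.8%, 72.9% and 46.5%.

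**The case against.** The strongest reply is that the gap belongs to a document not yet written. Protocol 8.3 makes the SAP the final authority on analysis, 8.4.3 leaves model detail to it, and a Part 2 SAP is announced. A sample-size section that names no model terms has not decided to omit one. This is right about where the fix belongs. But the protocol already plans this comparison and powers it at 90% on pooled placebo, and nothing supplied commits to an adjustment.

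The trigger is also narrow. If both Part 1 doses are repeated, every dose has concurrent placebo in both parts and the problem disappears. If one is repeated, the dropped Part 1 dose is still tested on Part 1 data alone under the current SAP. The main exposure is therefore a new Part 2 dose in the combined analysis. This limits the scope, although the protocol itself provides for the case.

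Third, the shifts are assumed. A shift of 1.0 is 83% of the whole assumed drug effect (1.0/1.2), and at 0.2 the damage is small. Both parts share one visit schedule, one set of eligibility criteria and a placebo run-in, and the gap between parts may be short. The rescue rule follows screening date, so study part is only a partial proxy for that change. These points bear on the likely size of a shift. They do not make the controls concurrent.

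**Conclusion.** The concern holds. The 90% is correct arithmetic for 64 v 128 but rests on an unstated assumption of equal placebo response in two separately randomised, sequential parts. If the pooled comparison is run as described, half of any shift passes into the estimate for a one-part dose, and control of Type I error at 0.05 is not assured. With an additive part term, power is about 86% and Type I error stays near 5% at all the shifts examined.

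The 86% assumes exactly one repeated dose, 64 evaluable subjects in each of six cells, SD 2.4, and a repeated dose whose effect over placebo is the same in both parts. The current protocol states no dropout allowance. The Type I error figures depend on assumed shifts and show sensitivity; they do not predict what will happen.

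**What to change.** In protocol 8.1 and 8.3 and in the Part 2 or final SAP:

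- Include study part, and part-by-visit in the MMRM, in any analysis that combines the parts, and make the part-adjusted estimate primary.
- Restate power for a one-part dose as about 86% in place of 90%, naming the assumptions (one repeated dose, additive part effect).
- Report the concurrent-placebo comparison (64 v 64, 80% power) as a sensitivity analysis, since it does not need the additive assumption.
- Report the unadjusted comparison with 128 placebo subjects as supportive only.

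This should be specified before Part 2 data exist. The cost is one model term with its visit interaction and a less favourable stated power. It needs no extra patients, leaves power for the repeated dose at 98%, and requires no change to the Part 1 SAP.

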# 8.2. Definitions of Analysis Sets

A detailed SAP will be developed prior to database lock.

### 8.2.1. Intent-to-Treat Analysis Set

The intent-to-treat analysis set is defined as all randomized subjects categorized by their randomized treatment group (whether or not they received study drug). The analysis population for the efficacy endpoints is the intent-to-treat population.

### 8.2.2. Safety Analysis Set

The safety analysis set includes all randomized subjects who receive at least 1 dose of randomized study drug. The safety analysis set will be used for evaluation of safety variables. Subjects who receive at least 1 dose of RTA 901 will be classified in the RTA 901 group. Subjects who are randomized and receive at least 1 dose of placebo and no dose of RTA 901 will be classified in the placebo group. Subjects in the Run-in phase who fail to randomize into the Treatment Period will not be included in the placebo group.

Safety and tolerability will be evaluated by AEs, SAEs, clinical laboratory test results, vital signs, ECG findings, physical examinations, and weight. All analyses of the safety data will be performed using the safety analysis set. Descriptive statistics will be presented by treatment group assignment in the safety analysis set. No formal statistical testing is planned for safety analyses.

# 8.3. Endpoints and Objectives

The SAP will describe in detail the methods used for the primary, safety, secondary, and exploratory endpoints and will serve as the final arbiter of all statistical analyses. The study endpoints are listed in Section 2.2.

Data will be summarized using descriptive statistics. Continuous data will be summarized with statistics such as mean, standard deviation, median, minimum, and maximum. Categorical data will be summarized using frequency counts and percentages.

If doses selected for Part 2 include any doses studied in Part 1 (ie, 10 or 80 mg), then the final analysis by dose group will be performed following final study database lock. Otherwise, if doses selected for Part 2 do not include doses studied in Part 1 then final analysis by dose group for Part 1 or Part 2 doses will be performed following the Part 1 or Part 2 database lock, respectively.

# 8.4. Methods for Statistical Analyses

### 8.4.1. Hypotheses

Primary hypothesis: There will be a greater mean reduction from baseline in NPRS pain intensity for the RTA 901-treated groups compared with placebo after 12 weeks of double-blind treatment.

### **8.4.2.** Closed Testing Procedure

The overall Type I error rate will be controlled at the 0.05 significance level. A hierarchical testing strategy to control the overall Type I error will be defined in the SAP.

### 8.4.3. Analysis of the Primary Variable(s)

The primary analysis will be performed using mixed model repeated measures (MMRM), and detail of the MMRM model will be specified in the SAP. Within the framework of the MMRM model, estimate and 95% CIs will be calculated for the mean changes within each treatment group as well as for the differences in mean changes relative to the placebo.

### 8.4.4. Analysis of the Secondary Variables

The secondary endpoints will be summarized, and analyses will be described in the SAP.

### 8.4.5. Subgroup Analysis

Subgroup analysis will be described in the SAP.

### 8.4.6. Interim Analysis

No interim analysis for efficacy or safety is planned.

### 8.4.7. Sensitivity Analysis

Sensitivity analyses will be described in the SAP.

### 8.4.8. Analysis of Safety Variables

The number and percent of subjects with an AE will be summarized for each treatment group. Changes from baseline to each scheduled time point for physical examinations, vital sign measurements, ECGs, clinical laboratory measurements, and body weight will be summarized by treatment group.

In addition, the number and percent of subjects with a predefined abnormality in clinical laboratory tests will be summarized by treatment group.

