### 4.1.2. Run-in Exclusion Criteria

- 1. Has neuropathy from a cause other than T1DM or T2DM;
- 2. Has a condition other than DPNP that could confound the assessment of pain (eg, fibromyalgia or regional pain caused by lumbar or cervical compression);
- 3. HbA1c > 11% at Screening;
- 4. Diabetic foot ulceration or infection within 90 days prior to Screening;
- 5. Has had more than 1 episode of ketoacidosis or hyperosmolar state requiring hospitalization within 90 days prior to Screening;

- 6. Has had more than 3 episodes of hypoglycemia requiring medical assistance within 90 days prior to Screening;
- 7. Any acute or chronic medical condition, or concurrent therapy (pharmaceutical or otherwise) which, in the opinion of the Investigator could potentially adversely impact subject safety, response to study drug, or interfere with study assessments;
- 8. Clinically significant and severe ophthalmologic disease, including but not limited to retinopathy, or visual field impairment which, in the opinion of the Investigator could potentially preclude enrollment in the study;
- 9. Serum aminotransferase (alanine aminotransferase [ALT] or aspartate aminotransferase [AST]) levels > 1.5× the upper limit of normal at Screening;
- 10. Has HIV or active hepatitis B or C virus infection;
- 11. History of malignancy within 3 years prior to Screening, except for non-melanoma skin tumor, cervical carcinomas in situ, or successfully treated malignancies in remission:
- 12. Unwilling to practice a protocol-specified acceptable method of birth control (both males who have partners of child-bearing potential and females of child-bearing potential) during Screening, while taking study drug, and for at least 30 days after the last dose of study drug is ingested (Section 6.7);
- 13. Females who are pregnant or breastfeeding;
- 14. Subject is, in the opinion of the Investigator, unable to comply with the requirements of the study protocol or is unsuitable for the study for any reason;
- 15. Known hypersensitivity to any component of the study drug;
- 16. Systolic blood pressure < 90 mmHg after a period of rest at Screening;
- 17. Pneumonia due to COVID-19 within 6 months prior to Screening or a history of COVID-19–related hospitalization within 6 months prior to Screening;
- 18. Known or suspected active drug or alcohol abuse, per Investigator judgement;
- 19. Use of the following medications:

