## 6.5. Overdose

An overdose is defined as a subject administering any dose as non-compliant (more than 120% of expected study drug visit to visit). Overall, the RTA 901 toxicity program has identified the liver and kidney as target organs at doses producing systemic exposures (based on AUC) at least 50-fold above those observed in humans at the highest planned clinical dose of 80 mg. The adverse effects on liver and kidney identified in GLP toxicity studies were associated with readily monitorable and standard clinical pathology evaluations and were reversible after drug discontinuation. Overall, safety margins of > 40-fold were established, based on systemic exposures (ie, AUCs) at the no observed adverse effect levels from the 3-month GLP toxicity studies in mice and monkeys and the systemic exposure (ie, AUC) at the highest dose in human subjects (ie, 80 mg).

Any overdose is required to be reported within 24 hours either as an AE or SAE. Overdose does not automatically make an AE serious, but if the consequences of the overdose are serious and meet the serious criteria (Section 6.2), the event must be reported as an SAE according to Section 6.4.

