# 6.8. Management of Elevated Aminotransferase Levels (ALT and/or AST)

If a subject's aminotransferases are elevated, follow the instructions outlined in Table 6.

Table 6: Management of Elevated Aminotransferase Levels (ALT and/or AST)

ALT and/or AST Level(s)	Dose Discontinuation (Yes/No)
> 8× ULN	
> 5× ULN for more than 2 weeks	
> 3× ULN with the appearance of fatigue, nausea, vomiting, right upper quadrant pain or tenderness, fever, rash, and/or eosinophilia (> 5%)	Yes
$> 3 \times \text{ULN } \underline{\text{and}}$ (TBL $> 2 \times \text{ULN } \underline{\text{or}} \text{ INR} > 1.5$ )	
> 3× ULN	No

Abbreviations: ALT=alanine aminotransferase; AST=aspartate aminotransferase; INR=international normalized ratio; TBL=total bilirubin; ULN=upper limit of normal

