7.2. Laboratory data

Laboratory data will be evaluated to determine the incidence of abnormalities that emerge during the study. Changes in laboratory evaluations will be presented relative to baseline, which is defined as the closet visit prior to the subject start of randomized treatment. Baseline value is defined as data collected which are prior to and/or on the date of the first dose, usually also the same day as the Day 1 visit. If there is more than one value on or before Day 1, then the last non-missing value prior to (including on) the date of first randomized dose will be used as the baseline value.

Shift analyses

Each hematology, blood chemistry, coagulation parameter will be flagged as "low" or "high" relative to the parameter's normal range or as "unknown" if no results is available. All visits with available results, including unscheduled visits, will be included in shift analysis.

For each urinalysis laboratory parameter, the number and percentage of participants experiencing post-dosing shifts to abnormal will be summarized.

Each hematology and chemistry value will be flagged as "low", "normal", or "high" relative to the normal ranges of the laboratory that performed the assay, or as "unknown" if no result is available. Each urinalysis value will be flagged as "positive", "negative", or "unknown" if no value is available.

Shift from baseline to high/low status for hematology and chemistry parameters and shifts from baseline to high/positive for urinalysis will be presented. In each summary, the denominator for

the percentage is the number of patients at risk for the shift. The number at risk for a shift to low is the number of subjects whose baseline value was not low and who had at least one post-baseline value. The number at risk for a shift to high is the number of subjects whose baseline value was not high and who had at least one post-baseline value. Subjects will be counted only once for each parameter and each type of shift regardless of how many post-dosing assessments had that type of shift. A shift to high includes normal to high, low to high, and unknown to high; a shift to low includes normal to low, high to low, and unknown to low. A shift to positive includes 'negative' to 'positive' and 'unknown' to 'positive'.

Summary of change from baseline and other analyses

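### SAP 7.2 neither defines nor tabulates the predefined laboratory abnormalities that Protocol 8.4.8 promises by arm, and its shift tables only partly fill the gap

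*Protocol*

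**What the plan says.** Protocol 8.4.8 lists change-from-baseline summaries and then adds that "the number and percent of subjects with a predefined abnormality in clinical laboratory tests will be summarized by treatment group". It gives no criteria. Protocol 8.3 says that the SAP "will serve as the final arbiter of all statistical analyses", so the definition has to come from there.

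SAP 7.2 plans three outputs for laboratory data:

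- Shift tables: "Shift from baseline to high/low status for hematology and chemistry parameters and shifts from baseline to high/positive for urinalysis will be presented". On the denominator: "The number at risk for a shift to high is the number of subjects whose baseline value was not high", provided that they also have a post-baseline value. On counting: "Subjects will be counted only once for each parameter and each type of shift". Unscheduled visits are included.
- Descriptive statistics by arm and visit, with minimum and maximum, for the observed value, change and percentage change. Only scheduled visits enter.
- A listing of abnormal values.

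SAP 7.3 (Table 5) and SAP 7.4 (Table 6) set numerical thresholds for vital signs and ECG. SAP Section 9 declares one departure from the protocol, the ITT definition.

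Protocol 4.1.2 excludes serum aminotransferase "levels > 1.5× the upper limit of normal at Screening". Protocol Table 6 (Section 6.8) works with ALT/AST above 8x ULN, "> 5× ULN for more than 2 weeks", above 3x ULN with symptoms, above 3x ULN with total bilirubin above 2x ULN or INR above 1.5, and above 3x ULN alone. Only the last row carries no dose discontinuation. Protocol 6.5 states that the toxicity program "has identified the liver and kidney as target organs".

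**The concern.** Change in laboratory measurements is part of the primary safety endpoint (Protocol 2.2.1.2). The protocol promises a second kind of laboratory summary on top of mean changes: how many subjects in each arm crossed a line fixed in advance. The SAP fixes such lines for vital signs and ECG but not for laboratory tests, and does not say that it has dropped the item.

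What remains is a shift count against the normal range. For aminotransferases that count has two weaknesses: it does not grade the rise, and it cannot register a rise in someone who starts above normal, a group that the entry criteria admit. At stake is a by-arm comparison at the aminotransferase levels that the protocol itself uses, including the joint pattern with bilirubin or INR.

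**Working it through.** The plan states no figure for this point, so the check compares texts and follows example subjects through the planned outputs.

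**1. Is there a predefined criterion?** Protocol 8.4.8 requires one. SAP 7.2 offers low, normal or high against the laboratory range, and positive or negative for urinalysis. It has no multiple of ULN, no grade and no joint category, and points to no criteria elsewhere.

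**2. Can subjects high at baseline be enrolled?** Yes. The limit in Protocol 4.1.2 leaves in anyone above ULN but not above 1.5x ULN at Screening. The randomization criteria (Protocol 4.2) set no aminotransferase limit. Chemistry is drawn on Day 1, which is usually the baseline under SAP 7.2.

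**3. Where does each hypothetical ALT course appear?**

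| Course | Shift to high | Maximum by arm and visit | AE and discontinuation tables | Listing |
|---|---|---|---|---|
| normal to 1.05x ULN | counted | unlikely to show | only if judged clinically significant | yes |
| normal to 9x ULN | counted, same as above | if at a scheduled visit and the arm's largest | expected | yes |
| 1.4x to 9x ULN | not counted | if at a scheduled visit and the arm's largest | expected | yes |
| 1.4x to 3.5x ULN, no symptoms, normal bilirubin and INR | not counted | if at a scheduled visit and the arm's largest | only if judged clinically significant | yes |

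The entry 'expected' rests on three provisions. Protocol Table 6 calls for dose discontinuation above 8x ULN. Protocol 6.3.2 makes a laboratory change an adverse event when action is required. SAP 7.1 tabulates adverse events leading to treatment discontinuation by dose level. The last row of the table shows the real gap: such a subject may be in no by-arm count at all.

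**4. Blindness to size (hypothetical values).** Take two arms of 64, with every subject normal at baseline. In arm A, 8 subjects rise to 1.2x ULN. In arm B, 4 rise to 1.2x and 4 reach 3.5x, 4x, 6x and 9x ULN.

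| Count | Arm A | Arm B |
|---|---|---|
| Shift to high | 8 (8/64 = 12.5%) | 8 (12.5%) |
| >3x ULN | 0 | 4 |
| >5x ULN | 0 | 2 |
| >8x ULN | 0 | 1 |

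The shift table is identical for the two arms; a threshold table separates them.

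**5. Subjects lost from the denominator.** The documents do not give the share above ULN at baseline, so it is an assumption. Number removed = 64 x share, rounded:

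| Assumed share | Removed per arm | Left at risk |
|---|---|---|
| 5% | 3 | 61 |
| 10% | 6 | 58 |
| 20% | 13 | 51 |
| 30% | 19 | 45 |

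Subjects with an unknown baseline stay in; only those already high (or already low, for shifts to low) leave.

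**The case against.** The best defense is that the protocol never defines a predefined abnormality, and that outside the normal range is a definition fixed in advance. SAP 7.2 counts subjects on it by arm, with unscheduled visits, and counting only new shifts is a conventional treatment-emergent approach. On that reading most of the promise is kept. What stands against it is that the count still omits subjects already abnormal in that direction at baseline, and that the SAP chose graded thresholds for the other two safety domains.

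The second defense is that the shift tables are not alone. Maxima, the listing and the adverse event tables do not exclude anyone for a high baseline. This stands, and it limits the point. A reader might infer that a subject going from 1.4x to 9x ULN is never counted, or that no planned table could show a large rise by arm. The documents do not support either: such a subject would be expected among the adverse events leading to discontinuation, and could set the arm's maximum. These outputs still do not give a count at set levels. A maximum is one value, a listing is not a comparison, and adverse events depend on the investigator's judgment when no action is triggered.

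A reader might also infer that Part 2 dose selection suffers. Protocol 3.6 and 4.5.2.3 base it on an exposure-response analysis for efficacy, under a separate charter and analysis plan, and nothing says that the SAP 7.2 tables feed it. Safety during the trial is watched by a data monitoring committee with unblinded data (Protocol 4.5.2.2). Nor should the target-organ statement be read as an expected human signal: Protocol 6.5 places those findings at exposures at least 50-fold above that at 80 mg, and describes them as monitorable and reversible.

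Last, the content of SAP Section 8 and the appendices is not visible, so a criteria table there cannot be excluded.

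**Conclusion.** The point holds as a gap between protocol and SAP in safety reporting. A by-arm count of predefined laboratory abnormalities is promised, no criterion beyond the normal range is given, and the change is not declared. The shift tables are a partial substitute: they ignore the size of a rise and omit subjects already abnormal in that direction. Two things are missing from every visible SAP table: by-arm counts at set aminotransferase levels, and a joint count of ALT/AST with bilirubin or INR. Rises above 3x ULN that trigger no action and are not judged clinically significant would not be counted by size anywhere.

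The size cannot be put as a number of missed cases, because the documents give neither an event rate nor the share of subjects high at baseline. An assumed event rate would show how often such rises occur, not what the tables hide. The 3 to 19 subjects per arm leaving the denominator are conditional on the assumed 5% to 30%. The conclusion does not depend on them, but it does assume that the parts of the SAP that cannot be seen hold no criteria table. It reaches neither the design nor safety monitoring during the trial.

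**What to change.** Add to SAP 7.2 one descriptive table by arm (n and %) of subjects with any post-baseline value, unscheduled visits included, in these categories: ALT or AST >3x ULN, >5x ULN and >8x ULN; and ALT or AST >3x ULN with total bilirubin >2x ULN or INR >1.5. Use all subjects with a post-baseline value as the denominator, whatever their baseline status. State whether the joint category requires values from the same sample. Note in the table that the >5x category takes the multiple from Protocol Table 6 without its two-week duration.

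These are reporting categories only and change no stopping rule. A kidney category, such as eGFR below the entry limit of 60 mL/min/1.73 m², is optional.

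If the sponsor prefers the normal-range definition, SAP 7.2 should say that this is the predefined abnormality, and Section 9 should record that no graded count will be given.

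The cost is one safety table. ALT, AST, total bilirubin and INR are already scheduled at Screening, Day 1 and every later visit (Protocol 5.3.6 and Table 4).
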